7.4 Anesthesia Monitoring

Invasive hemodynamic monitoring should be attempted prior to induction of GA to allow for tight hemodynamic control. To limit any delay in time to revascularization, attempts to establish peripheral invasive arterial access should be limited to 5 minutes; after that time, continuously-cycled non-invasive blood pressure measurements should be performed until invasive hemodynamic monitoring can be achieved through the femoral sheath. SBP should be maintained at 140 to 180 mmHg throughout with phenylephrine and/or norepinephrine as needed. Patients who are converted from sedation who already have invasive hemodynamic monitoring through the femoral sheath do not need additional arterial access.

End-tidal CO₂ concentration (PETCO₂) in patients receiving GA should be maintained at 35 to 40 mmHg (corresponding to a PaCO₂ ~40-45 mmHg).

All patients who are deemed medically appropriate for extubation should be awakened and extubation attempted at the conclusion of the procedure. Muscle paralysis should be reversed at the conclusion of the procedure using neostigmine or sugammadex; those patients with deep neuromuscular blockade that precludes reversal with neostigmine should be reversed with an adequate dose of sugammadex to avoid unnecessary prolonged intubation.

7.5 Anesthetic Data Collection

The following intra-procedural anesthesia variables will be collected:

- Anesthetic agents used for GA or sedation
- PETCO₂ q5 min in GA group.
- RASS score q15 min in sedation group.
- Oxygen saturation q15 min
- Continuous BP measurements from an electronic anesthetic record for determination of time spent with SBP <140 mmHg.
- Utilization of norepinephrine, phenylephrine, or other vasopressors as well as total dose administered.
- Documentation of post-procedure extubation or the reason for remaining intubated.
- Reason of crossover of anesthesia modality (sedation to GA) – patient agitation, airway difficulty, loss of consciousness, aspiration, cardiovascular instability

8.0 SAFETY

8.1 Adverse Events

An adverse event could include any of the following events, which develop or increase in severity during the course of the study:

- Any signs or symptoms whether thought to be related or unrelated to the condition under study;
- Any clinically significant laboratory abnormality;
- Any abnormality detected during physical examination.

These data will be recorded on the appropriate CRFs, regardless of whether they are thought to be associated with the study arm treatment. Signs or symptoms will be graded by the Investigator as mild, moderate or severe according to the following definitions:

Grade:	Definition
Mild:	Causing no limitation of usual activities
Moderate:	Causing some limitations of usual activities
Severe:	Causing inability to carry out usual activities.

8.2 Serious Adverse Events (SAEs)

A serious adverse event is defined as any event that suggests a significant hazard, contraindication, side effect or precaution. A serious adverse event includes any event that:

- Results in death;
- Is life threatening;
- Results in prolongation of existing hospitalization;
- Results in persistent or significant disability/incapacity;
- Important or significant medical events that require medical or surgical intervention, based upon appropriate clinical judgment.

The Investigator must assess the relationship of the adverse event to the study device using the following criteria categories and definitions:

- Unrelated - The adverse event is determined to be due to a concurrent illness or effect of another device/drug and is not related to the type of anesthesia utilized.
- Possible - The adverse event is determined to be potentially related to the treatments received for anesthesia and an alternative etiology is equally or less likely compared to the potential relationship to the type of anesthesia provided.
- Probable - There is a strong relationship to the type of anesthesia, or recurs on re-challenge, and another etiology is unlikely.
- Highly Probable - There is no other reasonable medical explanation for the event.

8.2.1 Reporting of Serious Adverse Events

Each clinical site will follow their internal policies for reporting SAEs to their IRB. In addition, sites will alert the UT-Houston data-core within 24-hours of becoming aware of the SAE. This alert will be relayed to the study PIs for review. If an SAE is confirmed, the coordinating site will be responsible for reporting to the DSMB as outlined in the DSMB charter. DSMB reports will be forwarded to all participating clinical sites for local IRB submission.

The study sponsor is responsible for the coding and reporting any adverse event required by regulatory authorities. The study sponsor will code AEs using MedDRA (Medical Dictionary for Regulatory Affairs). Unanticipated serious adverse events that meet criteria for FDA submission per 21 CFR part 803 will be submitted by the study sponsor.

8.3 Follow-Up of Adverse Events

All adverse events will be collected from the time of randomization and monitored until day 7 or hospital discharge, whichever occurs first. AEs that do not meet criteria for resolution will be categorized as on-going after day 7 or discharge.

9.0 STATISTICAL METHODS

The study will be conducted under a common umbrella protocol developed by UTHealth with the intention of combining data from all satellite centers for analysis. Each participating site will give utmost importance to follow the study protocol to maintain consistency in study execution at all centers. Detailed analysis plan for all pre-specified outcome measures are located in separate statistical analysis plan.

9.1 Sample Size Justification

A maximum of 260 patients, 130 per arm will be randomized. Assuming a neutral prior probability (centered at OR of 1.0, 95% prior interval: 0.3–3.0) for the intervention effect, the sample size provides 80% power that General Anesthesia improves outcome (lower ordinal mRS) compared to Sedation if the true OR is >1.50 . Monte Carlo simulations were performed using R to estimate the Bayesian power of the study for the primary outcome measure. We assumed a threshold of 80% posterior probability of the OR >1.0 to declare effectiveness. See Appendix II for summary of simulation results.

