3.0 STUDY ENDPOINTS

3.1 Primary Endpoint

The primary endpoint is a comparison of independent clinical outcome, defined as a modified ordinal Rankin Scale (mRS) at 90 days (scores 5 and 6 combined) among patients randomized to GA versus sedation. Primary analysis will be intention to treat (ITT) and adjusted for stratification variables.

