9.2 Statistical Analyses

Intent-to-treat analyses will be performed. To summarize the data, descriptive statistics will be used. Demographics, vital signs, laboratory variables, stroke type and duration from onset of symptoms will be summarized for each treatment arm. Vital signs taken during the treatment period will be displayed graphically. In addition to ICH, other medical events will be tabulated by body system and severity.

Primary analyses will focus on comparing GA (combining inhalational and IV anesthesia) to sedation. All analyses will be conducted under a Bayesian paradigm to obtain estimates of odds ratio (OR) for primary outcome (ordinal mRS), relative risk (RR) for binary outcomes, and probability of treatment benefit or harm (quantities that cannot be obtained from frequentist analyses). For the treatment effect, we will use a neutral prior centered at OR of 1.0 with 95% prior interval of 0.3-3.0. This prior assumes a priori equipoise and excludes large treatment effects. Weakly informative priors will be used for all other parameters to exclude large treatment effects.²⁴

Generalized linear mixed models will be used to analyze all outcomes and will include treatment group, terminal ICA occlusion and time from onset of symptoms (stratification variables) as covariates and center (stratification variable) as a random effect to account for center variability. For the primary outcome of ordinal mRS at 3 months (scores 5 and 6 combined), we will use an ordinal logistic model. For binary outcomes we will use log binomial (or logistic in case of non-convergence) models to directly estimate relative risks (or odds ratios) and 95% CIs. The prior for the treatment effect will be a Normal (0, $sd=0.57$) in the log OR/RR scale. The prior for the intercept will be Normal (0, $sd=10$) and Normal (0,1) for other covariates in the model. A half-Normal(0,1) prior will be used for the standard deviation of the center random effect. For non-binary outcomes, we will select the best fitting models and use neutral, weakly informative priors that exclude large treatment effects. We will examine residuals from each model to ensure reasonable adherence to the assumptions of the models.

If, despite randomization with stratification for center, tICA, and time from onset of symptoms, any important differences between intervention groups occur in baseline variables related to outcome, secondary analyses will be performed controlling for these factors.

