9.3 Missing Data

If patients are lost to follow-up at the 90-day end of study evaluation, the worst-case scenario will be entered into the database (i.e., mRS = 6). In the event that the percent of patients lost to follow-up exceeds 5%, we will use multiple imputation methods. This technique quantifies the uncertainty due to the missing data.

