Appendix II. Monte Carlo simulation results of Bayesian power

1. Primary outcome of ordinal mRS at 90 days

Based on data from 3 previous trials, we assumed rates of 10%, 14%, 11%, 19%, 18%, and 28% for mRS outcome categories of (0, 1, 2, 3, 4, 5+6) for Conscious Sedation group. Data from ANSTROKE trial was downweighted 50%. We assumed a treatment effect size corresponding to an OR=1.53 (GA group having better outcomes). We simulated 10,000 trials for two total sample sizes, N=265 and N=250 and assuming rates of follow-up of 100%, 98%, 97%, 95%, and 90%. We calculated power (Table 1) to declare benefit based on range of thresholds to declare effectiveness (i.e., $\Pr(\text{OR}>1)>\text{threshold}$). For analyses, we used a neutral prior centered at OR of 1.0 (95% CI: 0.3–3.0) for the treatment effect and ordinal logistic analysis detailed in Section 9.2. Assumed cross-over rate of CS group to GA group is 10%. Type I error rates are given in Table 2.

Table 1: Power under a neutral prior and cross-over rate of 10%.

$\Pr(\text{OR}>1)>$	N=265	N=260	N=257	N=250	N=245	N=242	N=238	N=225
0.95	0.50	0.49	0.49	0.48	0.47	0.47	0.46	0.44
0.90	0.66	0.64	0.64	0.64	0.63	0.62	0.62	0.60
0.85	0.74	0.73	0.73	0.73	0.72	0.72	0.71	0.70
0.80	0.81	0.80	0.80	0.80	0.79	0.79	0.78	0.77
0.75	0.85	0.85	0.84	0.85	0.84	0.83	0.83	0.82

Table 2: Type I error rates under a neutral prior and cross-over rate of 10%.

$\Pr(\text{OR}>1)>$	N=265	N=260	N=257	N=250	N=245	N=242	N=238	N=225
0.95	0.04	0.04	0.04	0.03	0.04	0.04	0.04	0.04
0.90	0.08	0.08	0.08	0.08	0.08	0.08	0.09	0.08
0.85	0.13	0.13	0.13	0.13	0.13	0.13	0.14	0.13
0.80	0.18	0.18	0.18	0.18	0.18	0.18	0.18	0.18
0.75	0.23	0.23	0.23	0.23	0.23	0.23	0.23	0.24

2. Secondary outcome of dichotomized mRS at 90 days

We assumed good outcome (mRS of 0-2) rates of 45% for General Anesthesia group and 35% for Conscious Sedation group. We simulated 10,000 trials for each of the sample sizes in Table 3 and calculated power to declare benefit based on range of thresholds to declare benefit (i.e., $\Pr(\text{RR}>1)>\text{threshold}$). For analyses, we used a neutral prior centered at RR of 1.0 (95% CI: 0.3–3.0) for the treatment effect and a log binomial model detailed in section 9.2.

Table 3: Power under a neutral prior and cross-over rate of 10%.

$\Pr(\text{RR}>1)>$	N=265	N=260	N=250	N=242	N=225
0.95	0.42	0.43	0.42	0.37	0.41
0.90	0.58	0.57	0.56	0.54	0.56
0.85	0.67	0.67	0.66	0.62	0.64
0.80	0.73	0.74	0.73	0.71	0.72
0.75	0.79	0.79	0.77	0.76	0.77

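### Section 9.1 states 80% power for a true OR above 1.50, but Appendix II obtained that figure at OR 1.53 before 10% crossover; on that basis power at 1.50 is about 78%

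*Combined protocol and SAP*

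**What the plan says.** Section 9.1 sets a maximum of 260 patients, 130 per arm, a neutral prior on the OR (95% interval 0.3 to 3.0) and success at a posterior probability above 80% that the OR exceeds 1. It then says that "the sample size provides 80% power that General Anesthesia improves outcome (lower ordinal mRS) compared to Sedation if the true OR is >1.50" and points to Appendix II.

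Appendix II gives the inputs behind the number. On the effect: "We assumed a treatment effect size corresponding to an OR=1.53 (GA group having better outcomes". On dilution: "Assumed cross-over rate of CS group to GA group is 10" (per cent). On size and follow-up, it simulated "two total sample sizes, N=265 and N=250 and assuming rates of follow-up of 100%, 98%, 97%, 95%, and 90" (per cent). Table 1 prints 0.80 at N=260 for the 0.80 threshold. No result is printed for OR 1.50.

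Section 3.1 says "Primary analysis will be intention to treat (ITT) and adjusted for stratification variables", and section 9.2 repeats "Intent-to-treat analyses will be performed". For a patient lost at 90 days, section 9.3 says "the worst-case scenario will be entered into the database (i.e., mRS = 6", and then: "In the event that the percent of patients lost to follow-up exceeds 5%, we will use multiple imputation methods".

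**The concern.** The summary sentence and the simulation it rests on use different odds ratios, and section 9.1 does not say which scale its OR is on. With crossover from sedation to GA, the OR before crossover is larger than the OR that an ITT analysis estimates. A reader of section 9.1 alone would conclude that any true OR above 1.50 has at least 80% power, and could not tell whether crossover is already allowed for.

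The second question is whether the power figure reflects the section 9.3 rule. Putting lost patients of both arms into the worst category pulls the arms together, and that costs more than losing the same patients from the denominator.

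What is at stake is the accuracy of the power statement that readers will quote, not the conduct of the trial.

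**Working it through.** **Inputs.** Sedation-arm rates for mRS 0, 1, 2, 3, 4, 5–6: 10, 14, 11, 19, 18, 28% (Appendix II). Crossover 10% (Appendix II). Prior on the log OR Normal(0, 0.57) (section 9.2). N=260, threshold 0.80 (section 9.1). Assumptions of this check: proportional odds, crossed-over patients have the GA outcome distribution, a normal approximation to the posterior, and no covariates or center effect.

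**Step 1: outcome distributions.** Multiply the sedation cumulative odds by 1.53. For mRS 0–2, 0.35/0.65 × 1.53 = 0.824, so 0.824/1.824 = 45.2%. The GA rates are 14.5, 18.0, 12.6, 19.1, 15.5, 20.3%. The ITT sedation arm is 90% sedation plus 10% GA: 10.5, 14.4, 11.2, 19.0, 17.7, 27.2%. The common OR fitted between these two arms is 1.465, so θ = ln 1.465 = 0.382.

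**Step 2: power formula.** The information on the log OR with 1:1 allocation is V = (N/12)(1 − Σp̄³), where p̄ is the mean of the two arms' rates. Here Σp̄³ = 0.0328, so V = 21.667 × 0.9672 = 20.96 and √V = 4.578. Success requires the posterior mean to exceed 0.8416 posterior SDs, which gives

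power = Φ(θ√V − 0.8416 × √(1 + 1/(0.57² V))).

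1/0.57² = 3.078, so the second term is 0.8416 × √(1 + 3.078/20.96) = 0.901.

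**Step 3: reproduce the plan.** OR 1.53 before crossover: Φ(0.382 × 4.578 − 0.901) = Φ(0.848) = 0.802 (Table 1: 0.80). Replacing 0.8416 by the normal quantiles for thresholds 0.95, 0.90, 0.85 and 0.75 gives 0.495, 0.647, 0.739 and 0.848 (Table 1: 0.49, 0.64, 0.73, 0.85). At θ = 0 the result is 0.184 (Table 2: 0.18). With no crossover, OR 1.53 would give about 0.85, which does not match. So crossover was applied on top of 1.53.

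**Step 4: change only the OR.** The last column simulates the same model, 100,000 trials per setting except where marked.

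| Setting, 260 analysed | ITT OR | Formula | Simulation |
|---|---|---|---|
| 1.53 before 10% crossover | 1.465 | 0.802 | 0.800 |
| 1.50 before 10% crossover | 1.440 | Φ(0.364 × 4.577 − 0.901) = 0.778 | 0.777 |
| 1.50 as the ITT OR | 1.500 | Φ(0.405 × 4.576 − 0.901) = 0.830 | 0.831 |
| 1.53, no crossover | 1.530 | 0.852 | 0.85 to 0.86 (10,000 to 40,000 trials) |

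The gap between 1.53 and 1.50 on the basis used is 0.800 − 0.777 = 2.3 points. Both figures come from one model.

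**Step 5: lost patients.** Randomized number times follow-up rate matches most Table 1 columns: 265 × 0.98 = 259.7 and 265 × 0.97 = 257.05; 250 × 0.98, 0.97, 0.95, 0.90 = 245, 242.5, 237.5, 225. (265 × 0.95, about 252, has no column.) That pattern suggests that lost patients were dropped. Under section 9.3, a fraction L in each arm moves to the worst category: p becomes (1 − L)p plus L in mRS 5–6. At L = 5% and OR 1.53 the common OR falls to 1.429 (θ = 0.357, V = 20.85), so power = Φ(0.357 × 4.567 − 0.902) = 0.766. Dropping the same 5% leaves 247 patients (V = 19.91) and gives Φ(0.382 × 4.462 − 0.904) = 0.788.

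| Simulated power, OR 1.53 before crossover, 260 randomized | 2% lost | 5% lost |
|---|---|---|
| Scored mRS 6 | 0.786 | 0.765 |
| Dropped (255, 247 analysed) | 0.797 | 0.789 |

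With OR 1.50 before crossover, the mRS 6 rule gives 0.765 and 0.741. With 1.50 as the ITT OR it gives 0.816 and 0.794. If every lost patient would have scored 5–6 anyway, the rule costs nothing, so the range at 5% loss and OR 1.53 is 0.765 to 0.800.

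**The case against.** The sentence can be defended. The simulated 1.53 does lie above 1.50, and 1.50 may be a rounding: the dichotomized scenario in Appendix II (45% against 35%) is itself an OR of (0.45/0.55)/(0.35/0.65) = 1.52. Because the primary analysis is ITT, reading 1.50 as the ITT OR is natural, and then 80% is conservative by about 3 points. All of this stands, and it is why the point is minor. What remains is that on the basis Appendix II actually used, ORs from 1.50 up to just below 1.53 have less than 80% power, and neither reading gives the printed pair of 80% and 1.50.

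A reader might infer that section 9.1 gives no basis for its power. It does: N, prior, threshold, method and a pointer to Appendix II. Only the scale of the OR and the crossover are missing. A reader might also infer that the Appendix II arithmetic is wrong. It is not; Table 1 reproduces.

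The gap is small beside the precision available. This check gives about 0.79 at N=250 where Table 1 prints 0.80, so about 1 point may be model difference. The Monte Carlo standard error of a Table 1 entry is only √(0.8 × 0.2/10,000) = 0.4 points, however, and the 2.3-point gap is a within-model comparison.

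On lost patients, dropping is inferred from column sizes; Appendix II does not state it. Section 9.0 refers to a separate analysis plan that could say more. The documents predict no loss rate, and section 6.3 allows home visits, telephone interviews and caregiver answers, so loss may be small.

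**Conclusion.** Section 9.1 attaches the 80% to the wrong OR for the simulation it cites. The 80% belongs to OR 1.53 before 10% crossover, or an ITT OR of about 1.47. At 1.50 before crossover it is about 78%; at 1.50 as the ITT OR it would be about 83%. This is well supported, because the same model reproduces the N=260 column of Table 1 to within about 1 point at all five thresholds, and the type I error as well.

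The lost-patient point is weaker. If the mRS 6 rule was not simulated, it lowers power at OR 1.53 by about 1 point at 2% loss and about 3.5 points at 5%, of which about 2 points at 5% are beyond the cost of dropping the same patients. This assumes loss equal in both arms and unrelated to outcome, and it can shrink to nothing if lost patients would have scored 5–6.

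The stronger inference, that the trial is materially underpowered or that 260 is wrong, is not supported. The shift is 2 to 3 points, its direction depends on which OR was meant, and the sample size, analysis and decision rule are unaffected.

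**What to change.** Restate section 9.1 as about 80% power at OR 1.53 before 10% sedation-to-GA crossover (ITT OR about 1.47) with 260 analysed, and about 78% at OR 1.50 before crossover. If 1.50 was meant as the ITT OR, say so and give about 83%.

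In Appendix II, state how lost patients were handled. Rerun the existing simulation for 260 randomized under the section 9.3 rule and report power over 0–5% loss, with the loss assumptions stated.

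The cost is one sentence and a rerun of existing code, with no extra patients and no change to the analysis or the success criterion.

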9.2 Statistical Analyses

Intent-to-treat analyses will be performed. To summarize the data, descriptive statistics will be used. Demographics, vital signs, laboratory variables, stroke type and duration from onset of symptoms will be summarized for each treatment arm. Vital signs taken during the treatment period will be displayed graphically. In addition to ICH, other medical events will be tabulated by body system and severity.

Primary analyses will focus on comparing GA (combining inhalational and IV anesthesia) to sedation. All analyses will be conducted under a Bayesian paradigm to obtain estimates of odds ratio (OR) for primary outcome (ordinal mRS), relative risk (RR) for binary outcomes, and probability of treatment benefit or harm (quantities that cannot be obtained from frequentist analyses). For the treatment effect, we will use a neutral prior centered at OR of 1.0 with 95% prior interval of 0.3-3.0. This prior assumes a priori equipoise and excludes large treatment effects. Weakly informative priors will be used for all other parameters to exclude large treatment effects.²⁴

Generalized linear mixed models will be used to analyze all outcomes and will include treatment group, terminal ICA occlusion and time from onset of symptoms (stratification variables) as covariates and center (stratification variable) as a random effect to account for center variability. For the primary outcome of ordinal mRS at 3 months (scores 5 and 6 combined), we will use an ordinal logistic model. For binary outcomes we will use log binomial (or logistic in case of non-convergence) models to directly estimate relative risks (or odds ratios) and 95% CIs. The prior for the treatment effect will be a Normal (0, $sd=0.57$) in the log OR/RR scale. The prior for the intercept will be Normal (0, $sd=10$) and Normal (0,1) for other covariates in the model. A half-Normal(0,1) prior will be used for the standard deviation of the center random effect. For non-binary outcomes, we will select the best fitting models and use neutral, weakly informative priors that exclude large treatment effects. We will examine residuals from each model to ensure reasonable adherence to the assumptions of the models.

If, despite randomization with stratification for center, tICA, and time from onset of symptoms, any important differences between intervention groups occur in baseline variables related to outcome, secondary analyses will be performed controlling for these factors.

For the primary outcome of ordinal mRS at 3 months, a secondary analysis will be conducted comparing CS to inhalational anesthesia and to IV anesthesia adjusting for the stratifying variables. Models and priors will be the same as for the primary analysis.

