3.4 Exploratory Analyses

- 1) Ordinal ITT and as-treated analysis of primary outcome comparing three groups (CS, GA IV, GA inhalational) adjusting for stratification variables.
- 2) Multivariable adjusted analysis (including stratification variables) for both primary (mRS 0-2) and ordinal analysis of 90-day mRS outcomes, to include (but not limited to) baseline variables known to be clinically associated with stroke outcomes:
 - a. Age
 - b. NIHSS
 - c. Time from stroke onset-to-EVT groin puncture
 - d. IV-tPA treatment before EVT
 - e. Atrial Fibrillation
- 3) Duration of time during EVT spent below a systolic blood pressure of 140mmHg.
- 4) Total ICU and ventilator days.
- 5) Subgroup analyses to test for heterogeneity in patient benefit and Provider Skill:
 - a. Proximal vs. Distal occlusion location (ICA+M1-MCA vs. others)
 - b. High-volume vs. low-volume centers
- 6) Costs from a health system perspective

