4.2 Enrollment and Randomization

Enrollment in this study is defined as the moment when the randomization process is completed and the subject is assigned to a study arm. After randomization, no crossover is permitted unless either the neurovascular interventionalist or anesthesiologist determines the patient meets criteria as described in section 5.0. Randomization will occur via a secure, password-protected, web-based system. Subjects will be randomized 1:1 to GA or Sedation using permuted blocks and stratified by center, terminal ICA occlusion (yes/no), and time of stroke symptom onset (≤ 6 hours or 6-16 hours). Patients randomized to GA will subsequently be randomly assigned in a 1:1 ratio to either inhalational or IV anesthesia.

Stroke management and endovascular therapy procedures will occur as per local site usual care. Only FDA-approved thrombectomy devices should be used with first line use of stent retriever. Both general anesthesia and Sedation should be delivered and managed by an anesthesiologist.

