5.0 STUDY POPULATION

5.1 Inclusion Criteria

1. Acute ischemic stroke due to large intracranial vessel occlusion demonstrated on CT-angiography in the following anterior circulation locations that will be treated by endovascular therapy (EVT):
 - a. Internal Carotid Artery (terminal “T” or “L-type”- occlusion)
 - b. Middle Cerebral Artery (MCA) M1 or proximal M2
 - c. Anterior Cerebral Artery (ACA) A1 or proximal A2
 - Patients who receive IV-tPA thrombolysis are eligible provided the drug was delivered within 4.5 hours of stroke onset or last seen normal and in accordance with local hospital standard of care.
 - Patients who receive TNKase are also eligible, given that drug was delivered in accordance with the local hospital standard of care.
2. Ages 18-90.
3. National Institute of Health Stroke Scale (NIHSS) score 6-30
4. Time of stroke symptom onset of last seen normal to start of EVT (defined as groin puncture) \leq 16 hours.
5. Limited infarct core, as defined below and adapted from the 2018 American Heart Association guidelines²⁸
 - a. For patients presenting \leq 6 hours from time of symptom onset or last seen normal, Alberta Stroke Program Early Computed Tomography Score (ASPECTS) \geq 6
 - b. For patients presenting $>$ 6 hours and \leq 16 hours from time of symptom onset or last seen normal, they must satisfy EITHER ONE of the two following criteria:
 - i. Ischemic core by CT Perfusion or MRI/MR Perfusion $<$ 70 mL, a ratio of volume of penumbral tissue to infarct core of \geq 1.8, and absolute volume of penumbral tissue of \geq 15 mL²⁹

OR

- ii. For patients with NIHSS \geq 10, infarct core of $<$ 31 mL by CT Perfusion or MRI; For patients with NIHSS \geq 20, infarct core $<$ 51 mL.³⁰
6. Subject willing/able to return for protocol required follow up visits.
7. No significant pre-stroke disability (modified Rankin Score must be \leq 2).
8. Females of childbearing potential must have a negative serum or urine pregnancy test.
9. Patient or patient’s legally authorized representative has given Informed Consent according to Good Clinical Practices (GCP) and/or local IRB policies.

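### Age and baseline NIHSS, which the plan itself calls prognostic, are left out of the primary ordinal mRS model: a missed efficiency at N=260, not an error

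*Combined protocol and SAP*

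**What the plan says.** Section 3.1: "Primary analysis will be intention to treat (ITT) and adjusted for stratification variables". Section 9.2 gives the model: the analyses "will include treatment group, terminal ICA occlusion and time from onset of symptoms (stratification variables) as covariates", with center as a random effect. These are the three randomization factors of section 4.2. Age and NIHSS are not among them.

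Age and NIHSS appear as the first two items of an exploratory multivariable analysis in section 3.4, "to include (but not limited to) baseline variables known to be clinically associated with stroke outcomes". Section 9.2 offers one other possible route: if "any important differences between intervention groups occur in baseline variables related to outcome, secondary analyses will be performed controlling for these factors".

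Both values are known before randomization, because section 5.1 sets an age range of 18 to 90 and requires "National Institute of Health Stroke Scale (NIHSS) score 6-30". Section 9.0 adds a caveat: "Detailed analysis plan for all pre-specified outcome measures are located in separate statistical analysis plan". That separate plan is not in the text reviewed and may say more.

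**The concern.** In a trial of 260 patients with an ordinal functional outcome, strong baseline predictors are the cheapest source of power. The plan names two, holds both for every patient, and leaves both out of the analysis that decides the trial. Neither is a stratification factor, so neither the design nor the primary model deals with chance imbalance in age or severity.

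The imbalance-triggered analysis does not fill the gap. It is secondary, so it cannot change the primary result. Imbalance is also the wrong trigger, because adjusting for a prognostic covariate adds precision even when the arms are balanced.

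At stake is power that only just meets its 80% target. The threshold already accepts a null success rate of 0.18, so raising power by loosening the threshold would be unattractive. Adjustment raises power without touching it.

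**Working it through.** **Inputs from the documents.** N=260, 1:1 (section 9.1). Appendix II: CS rates 10/14/11/19/18/28% for mRS 0, 1, 2, 3, 4, 5+6; OR 1.53; 10% crossover from CS to GA. Success if Pr(OR>1) > 0.80. Treatment prior Normal(0, 0.57) on the log OR (section 9.2).

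**Step 1: reproduce the plan's figures (closed form).**
- GA rates at OR 1.53 are 14.5/18.0/12.6/19.1/15.5/20.3%. The CS arm is a 90/10 mixture of the CS and GA rates. The effective OR is 1.464, log 0.381.
- Information: V = (N/12)(1 − Σp̄³) = (260/12)(1 − 0.0328) = 20.96, so the SE is 1/√V = 0.218.
- Prior precision is 1/0.57² = 3.08. Success requires b·V/√(V + 3.08) > 0.842, so b > 0.842 × √24.03 / 20.96 = 0.197.
- Power = Φ((0.381 − 0.197)/0.218) = 0.801. The plan states 0.80.
- Under the null, V = 20.81 and the success rate is 0.184. The plan states 0.18.
- At thresholds 0.95, 0.90, 0.85 and 0.75 the closed form gives 0.493, 0.645, 0.737 and 0.847, against 0.49, 0.64, 0.73 and 0.85 in Appendix II Table 1.

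**Step 2: assume a range of prognostic strength.** The documents give none. Age and NIHSS are given equal coefficients β per SD, with R² = 2β²/(2β² + π²/3). Values of 0.29, 0.43, 0.64 and 0.84 give R² of 0.05, 0.10, 0.20 and 0.30.

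**Step 3: simulate.** There were 6,000 individual-level proportional-odds trials per cell (Monte Carlo SE about 0.005; paired SE of each gain 0.003-0.005). Each trial had 12 unequal centers and permuted blocks of 4 within center by tICA by onset stratum. Fits used the section 9.2 priors with a Laplace approximation. Further assumptions: tICA 25%; onset beyond 6 hours 35%; and either log ORs of 0.4 (tICA) and 0.2 (late onset), center SD 0.3 and NIHSS 0.4 SD higher with tICA, or all four set to zero. Entries are power for strata-only → adjusted at threshold 0.80.

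| Scenario | R² 0.05 | 0.10 | 0.20 | 0.30 |
|---|---|---|---|---|
| 1.53 marginal, strata and center prognostic | 0.81 → 0.83 | 0.81 → 0.84 | 0.80 → 0.86 | 0.80 → 0.89 |
| 1.53 marginal, strata and center not prognostic | 0.80 → 0.81 | 0.80 → 0.83 | 0.80 → 0.85 | 0.79 → 0.88 |
| 1.53 covariate-conditional: strata-only | 0.78 | 0.76 | 0.72 | 0.68-0.69 |
| 1.53 covariate-conditional: adjusted | 0.78-0.80 | 0.78-0.80 | 0.78-0.80 | 0.78-0.80 |
| Marginal, 5% lost at random and coded mRS 6 (section 9.3) | 0.77 → 0.79 | 0.77 → 0.80 | 0.77 → 0.83 | 0.76 → 0.86 |

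- Null success rate: 0.18-0.19 for both models.
- No prognostic value at all: 0.81 for both models, so nothing is lost.
- Misspecified case (true age effect a step, true NIHSS effect flat above +0.3 SD, both modelled as linear): 0.810 → 0.829 at R² 0.10 and 0.806 → 0.845 at 0.20.
- Trial by trial, in the first row, adjustment gains a success in 3.6%, 5.5%, 8.7% and 11.0% of trials and loses one in 1.9%, 2.5%, 2.5% and 2.2%.
- Equivalent N is 260 × (ratio of mean posterior z)². Ratios squared of 1.06, 1.13, 1.27 and 1.44 give about 276, 293, 330 and 375.

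**Step 4: cross-check.** A separate simulation of 20,000 trials per scenario, without center or strata, moved power from about 0.80 to 0.81, 0.83, 0.855 and 0.88, with a null rate of 0.18-0.19. In that simulation the gain could instead be spent on the threshold. At 80% power it could rise to about 0.81, 0.83, 0.85 or 0.88, and the null rate would fall to about 0.17, 0.16, 0.13 or 0.10.

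**The case against.** The strongest reply is that this is a preference, not a defect. Adjusting for exactly the randomization factors is coherent and pre-specified, and it gives no bias. That is right, and it is why the point is graded as a missed efficiency.

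The size of the gain rests on an assumed R², on other assumed inputs, and on which reading of 1.53 the sponsor intended. That stands too. The 0.01-0.02 end of the range cannot be excluded, and the equivalent sample sizes are illustrative. Under the conditional reading, adjustment avoids a loss and does not add to planned power. The direction of the gain does not depend on these choices, because the plan itself says the two variables are associated with outcome.

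The 0.80 power is also not on a knife edge: Appendix II Table 1 still shows 0.80 at N=250, 0.79 at 242 and 0.77 at 225. This is fair, though 0.80 remains the stated figure at the planned N.

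The plan does contain an exploratory adjusted analysis and an imbalance-triggered one, and a separate SAP may add detail. Neither analysis can alter the primary result, and a SAP that adds covariates would have to be reconciled with sections 3.1 and 9.2.

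Finally, at Version 5.0 the change may come too late. The documents do not give accrual status, so the recommendation has to be conditional.

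**Conclusion.** The concern holds as a missed efficiency. The primary model is valid and its stated operating characteristics reproduce. Leaving out age and NIHSS costs between about 1 and 9 points of power on the marginal reading, for assumed R² of 0.05 to 0.30. On the conditional reading it leaves the strata-only model at 0.78 down to about 0.68. In every case examined the null success rate is the same for both models, and there is no loss if the covariates turn out to be uninformative. The direction is secure; confidence in the magnitude is moderate, because the documents give no prognostic strength. The change is worth making if it can still be made without knowledge of outcomes by arm.

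**What to change.** Add age and baseline NIHSS to the primary ordinal model and the section 9.5 interim model, alongside tICA, onset stratum and center. Enter both as continuous and standardized, to suit the Normal(0,1) covariate prior. State that the OR is then conditional on them, rerun the ordinal tables in Appendix II, and keep the strata-only model as a sensitivity analysis. Keep the imbalance-triggered analysis for other baseline variables.

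Make this change only if those setting the model have seen no outcome comparison by arm. The safety looks at 100 and 200 patients compare death, which is part of the combined 5+6 category, and the efficacy look is at 132. The un-blinded biostatistician described in section 11.2 should not set the model. If such a comparison has been seen, keep the current primary model and make the age- and NIHSS-adjusted model a named key secondary analysis with a closed covariate list.

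**Cost.** No new data. The wording changes in sections 3.1, 9.2, 9.5 and the SAP. Sections 3.2 and 3.4 and the three-group comparison closing section 9.2 need conforming edits, because they also refer to stratification variables. The reported OR becomes covariate-conditional (about 1.55 to 1.72 when the marginal OR is 1.53), and the Normal(0, 0.57) prior then applies on that scale; the simulated gains already include it. In roughly 2% to 2.5% of simulated trials the adjusted model loses a success that the strata-only model would have declared.
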